1L osimertinib treatment, the ORR was CCI (95%CI: CCI), the median DoR was CCI (95% CI: CCI), and the median PFS was CCI (95% CI: CCI). There were CCI patients who were considered responders among CCI evaluable patients at the savolitinib 300 mg bid combination regimen with IHC90+ and/or FISH10+ status. Responses at the savolitinib 600 mg od combination regimen with IHC90+ and/or FISH10+ status were not assessed.

This clinical observation is consistent with and supported by the evidence shown in other clinical studies in NSCLC and in nonclinical models, suggesting that MET amplification is sufficient to confer resistance to EGFR TKI therapy (Bean et al 2007, Engelman et al 2007, Turke et al 2010), and resistance can be associated with high level of MET protein expression (Bean et al 2007, Turke et al 2010, Wu et al 2018, Wu et al 2020, Scagliotti et al 2020, Wolf et al 2020, Hartmaier et al 2021). Since MET-mediated resistance is expected to provide EGFR-bypass growth signalling in a cell intrinsic manner, during the development of resistance, tumour cell growth that is dependent on MET signalling is expected to undergo clonal selection and dominate the cellular population in the fully resistant tumour. Thus, elevated cut-offs are likely to more accurately identify tumours with more homogeneous dependence on MET signalling.

Based on this biological rationale and ad hoc exploratory analysis results, higher MET cut-offs (ie, FISH10+ and/or IHC90+) are considered more appropriate to identify the target patient population that will potentially benefit from the novel combination treatment. Therefore, under CSP version 7.0, only MET amplified/overexpressed (FISH10+ and/or IHC 90+) patients will be enrolled.

[figure not shown]
The safety data from the most recent data review (as of 27 August 2021) for all patients who received at least one dose has shown that overall, the safety profile of savolitinib in combination with osimertinib is tolerable and manageable at 300 mg od, 300 mg bid and 600 mg od doses. CCI

CCI

not related to study drug) CCI

[figure not shown]
No new safety findings have been identified, including at the 300 mg bid dose (n=37) with a median duration of exposure of

approximately 2.6 months. **CCI**

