
To determine the efficacy of savolitinib (300 mg od, 300 mg bid, and 600 mg od, respectively) in combination with osimertinib in patients with EGFRm+, MET-amplified/overexpressed (FISH5+ and/or IHC50+)^b, locally advanced or metastatic NSCLC who have progressed following osimertinib.
	
 • ORR (except 300 mg od), DoR, and PFS by investigator assessment in accordance with RECIST 1.1. • OS

To determine the efficacy of (1) 300 mg od, 300 mg bid and 600 mg od of savolitinib in combination with osimertinib in patients with EGFRm+ MET amplified/overexpressed (FISH 10+ and/or IHC90+)^{a,b}; (2) 300 mg od, 300 mg bid and 600 mg od of savolitinib in combination with osimertinib in patients with EGFRm+ MET amplified/overexpressed (FISH5+ and/or IHC50+)^b (3) savolitinib 300 mg bid in combination with osimertinib and savolitinib 300 mg bid in combination with placebo, respectively, in patients with EGFRm+ MET amplified/overexpressed (FISH10+ and/or IHC90+)^a following treatment with 1L osimertinib.
	
 • ORR, DoR, and PFS assessed by BICR in accordance with RECIST 1.1

To assess the impact of savolitinib and osimertinib on disease-related symptoms and HRQoL in this patient population.
	
 • Mean change from baseline in EORTC QLQ-C30 and QLQ-LC13.

To evaluate the pharmacokinetics of osimertinib and savolitinib in this patient population.
	
 • Plasma concentrations of osimertinib, savolitinib and their metabolites.

To determine the prevalence of ctDNA clearance after osimertinib and savolitinib treatment in this patient population.
	
 • Total clearance in EGFR mutations at 6-weeks after therapy initiation (percentage and absolute change from baseline in EGFR mutation allele frequencies).

Safety Objectives:	Endpoints:
To evaluate the safety and tolerability of savolitinib in combination with osimertinib and savolitinib in combination with placebo.	
 • AEs, SAEs and discontinuation rate due to AEs. • Clinical chemistry/haematology including LFTs. • ECHOs, ECGs and vital signs including blood pressure and heart rate.
Exploratory Objectives:	

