9.4.4 Safety analyses

The SAF will be used as the population for reporting safety for patients dosed under all CSP versions (see Section 9.3 for analysis set definitions).

Safety and tolerability will be assessed in terms of AEs, deaths, laboratory data, vital signs, ECG data and ECOG performance status.

The Medical Dictionary for Regulatory Activities (MedDRA) will be used to code AEs. AEs will be graded according to the National Cancer Institute CTCAE (Version 5.0).

The number of patients experiencing each AE will be summarised by the MedDRA system organ class and preferred term. The number and percentage of patients with AEs in different categories (eg, causally related, CTCAE Grade ≥ 3 etc) will be summarised, and events in each category will be further summarised by MedDRA system organ class and preferred term. SAEs will be summarised separately if a sufficient number occur.

Any AE occurring before the first dose of study drug will be included in the data listings but will not be included in the summary tables of AEs. AE summary tables will include only treatment-emergent adverse events. AEs will be defined as treatment emergent if they have an onset, or worsen (by investigator report of a change in intensity), during the study treatment period (defined from date of first dose of any study treatment to date of last dose of any study treatment) or safety follow-up period (28 days [± 7 days] after last dose of study treatment).

Any events in this period that occur after a patient has received further therapy for cancer (following discontinuation of IP) will be flagged in the data listings.

Discontinuation rate due to AEs will be summarised for the first 6 weeks and at any time.

During the evaluation of the AE data, an AstraZeneca medically qualified expert will review the list of AEs that were not reported as SAEs and AEs leading to discontinuation. Based on the expert's judgement, significant AEs of particular clinical importance may, after consultation with the Global Patient Safety Physician, be considered other significant adverse events and reported as such in the clinical study report. A similar review of laboratory/vital signs (pulse and BP)/ECG data will be performed for identification of other significant adverse events.

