2.2 Analysis Sets

The analysis sets are presented in [Table 2](#).

Patients will be assigned to each of the populations in Table 2 and to the diagnostic populations (centrally confirmed by FISH [FISH5+, FISH10+] and centrally confirmed by IHC [IHC50+, IHC90+]), prior to any analyses being performed. Additional details on diagnostic populations can be found in section [4.1](#).

Table 2 Analysis Sets

Analysis Set	Definition
Target Population Analysis Set (TPAS)	All patients assigned to savolitinib 300 mg bid + osimertinib who have FISH10+ and/or IHC90+ status, have progressed following 1L osimertinib, and have taken ≥ 1 dose of either study drug.
Contribution of Components Analysis Set (CAS)	All patients randomised under CSP version 7.0 with treatment groups assigned in accordance with the randomisation, regardless of the treatment actually received.
Safety Analysis Set (SAF)	All enrolled patients who take ≥ 1 dose of either study drug.
PK Analysis Set	All patients who receive at least 1 dose of savolitinib or osimertinib as per the protocol for whom any post-dose PK data are available and do not violate or deviate from the protocol in ways that would significantly affect the PK analyses will be included in the PK analysis set.
Evaluable for Response	Dosed patients who have measurable disease at baseline. This population will only be used for interim analyses.
Evaluable for Response 2	Dosed patients with measurable disease at baseline who have had the opportunity for 2 on-treatment RECIST scans. This population will only be used for interim analyses.
Safety Analysis Set 2 (SAF2)	All enrolled patients who take ≥ 1 dose of either study drug who have had the opportunity to be treated for 6 weeks. This population will only be used for interim analyses.

CSP Clinical study protocol; FISH Fluorescence in situ hybridisation; IHC immunohistochemistry; PK Pharmacokinetic(s); RECIST Response Evaluation Criteria in Solid Tumor.

If during the study a patient stops one of the two study treatments and continues on monotherapy or a patient crossover to the combo treatment, the data for the patient will continue to be treated as per the initial treatment allocation.

For the Pharmacokinetic [PK] analysis set, where a protocol deviation impacts only part of a patient's data, the affected portion of the patient's PK data will be excluded from PK analysis and summary statistics, and the remaining valid data will be utilised.

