4 ANALYSIS METHODS

4.1 General principles

The below mentioned general analyses principles will be followed throughout the study:

- Statistical tests will be performed for two-sided hypothesis. All confidence intervals [CI] will use a 95% confidence level unless otherwise stated.
- Descriptive statistics will be used for all variables, as appropriate. Continuous variables will be summarised by the number of observations, mean, standard deviation [SD], median, quartiles (Q1 and Q3), minimum, and maximum. For log transformed data geometric mean [Geomean], geometric SD [gSD], geometric coefficient of variation [gCV%], median, minimum and maximum will be presented. Categorical variables will be summarised by frequency counts and percentages for each category.
- Unless otherwise stated, percentages will be calculated out of the analysis set total.
- Unless otherwise stated, for continuous data, mean, Geomean, median, quartiles as well as LSmeans will be rounded to 1 additional decimal place compared to the original data. The SD, gSD and standard error [SE] will be rounded to 2 additional decimal places compared to the original data. Minimum and maximum will be displayed with the same accuracy as the original data.
- For categorical data, percentages will be rounded to 1 decimal place.
- Ratio and CI of the ratio will be rounded to two decimal points
- P-values will be presented to three decimal points (displayed as “<0.001” for p-values lower than 0.001).
- SAS® version 9.4 (or higher) will be used for all analyses.
- There are two diagnostic populations of analytical interest as follows:
 - All Patients (FISH5+ and/or IHC50+): This population includes patients identified by lower MET biomarker cut offs (≥ 5 MET gene copies or MET:CEP7 ratio ≥ 2 [FISH5+] and/or $\geq 50\%$ of tumour cells staining at strong 3+ intensity [IHC50+])
 - FISH10+ and /or IHC90+: This population includes patients identified by higher MET biomarker cut offs (≥ 10 MET gene copies according to central MET FISH test [FISH10+] and/or $\geq 90\%$ of tumour cells staining at strong 3+ intensity according to central MET IHC test [IHC90+])

The populations are not mutually exclusive, i.e. a patient may be a member of both populations.

- Analyses will be presented by the assigned dosing regimen (i.e., savolitinib starting dose: 300 mg od, 300 mg bid and 600 mg od (in combination with osimertinib), or 300 mg bid + placebo.

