4.2.3 Safety and Tolerability Data

Unless otherwise stated, analysis of safety data will be based on SAF for patients dosed under all CSP versions as follows:

- savolitinib (300 mg od, 300 mg bid and 600 mg od, respectively) in combination with osimertinib in patients with EGFRm+, MET amplified/overexpressed (FISH10+ and/or IHC90+), locally advanced or metastatic NSCLC who have progressed following osimertinib
- savolitinib (300 mg od, 300 mg bid and 600 mg od, respectively) in combination with osimertinib in patients with EGFRm+, MET amplified/overexpressed (FISH5+ and/or IHC50+), locally advanced or metastatic NSCLC who have progressed following osimertinib
- savolitinib in monotherapy (i.e., 300 mg bid + placebo)

Dedicated analysis for patients randomised under CSP version 7.0 may be performed.

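### SAP 4.2.3 makes the by-arm safety summary of version 7.0 patients optional, so the placebo column is committed only beside a combination column that mixes protocol versions 5.0 to 7.0

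*SAP*

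**What the plan says.** The safety objective covers two regimens: "To evaluate the safety and tolerability of savolitinib in combination with osimertinib and savolitinib in combination with placebo" (Protocol section 3).

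SAP 4.2.3 opens: "Unless otherwise stated, analysis of safety data will be based on SAF for patients dosed under all CSP versions as follows". Three groups of rows follow: each combination regimen in patients who are FISH10+ and/or IHC90+, each combination regimen in patients who are FISH5+ and/or IHC50+, and savolitinib 300 mg bid + placebo. The section ends: "Dedicated analysis for patients randomised under CSP version 7.0 may be performed".

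The SAF is defined in SAP 2.2 as "All enrolled patients who take ≥ 1 dose of either study drug", with no restriction by version, line of therapy or randomisation. Protocol 9.4.4 agrees: "The SAF will be used as the population for reporting safety for patients dosed under all CSP versions". The safety row of SAP Table 3 also uses the SAF, and SAP 4.2.3.1 presents exposure on the Target Population Analysis Set and the SAF. The set of patients randomised under version 7.0 (CAS) is used for baseline characteristics, ORR, DoR, PFS and the CNS endpoints, but for no committed safety or exposure table.

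Doses are kept apart: "Analyses will be presented by the assigned dosing regimen" (SAP 4.1).

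**The concern.** Under version 7.0 the trial randomises patients 2:1, double blind, to savolitinib 300 mg bid with osimertinib or with placebo. Those two groups share entry criteria, calendar period and blinding, so they are the natural basis for describing what osimertinib adds to toxicity. The plan reports efficacy in them but need not report adverse events in them.

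A reader of the study report will look at the savolitinib + placebo column and the 300 mg bid + osimertinib column together, because the safety objective names both regimens. As committed, the second column contains patients from earlier versions who differ from the first in ways that can bear on adverse events and on how they are attributed. SAP 4.2.3.2 tabulates events by the investigator's view of their relation to osimertinib, and that judgement is made open label in one part of the column and blinded in the other.

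**Working it through.** There is no stated figure to reproduce: neither document sets a sample size, power or error rate for safety, and the version 7.0 arm sizes are redacted. The check sets the two columns side by side and then gives a scale.

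| Feature | 300 mg bid + placebo | 300 mg bid + osimertinib |
|---|---|---|
| Versions contributing (SAP 2.1) | 7.0 | 5.0, 6.0 and 7.0 |
| Blinding (Protocol 1.2, 6.3) | double blind | open label under 5.0 and 6.0, double blind under 7.0 |
| Allocation (SAP 2.1) | randomised against the combination | same under 7.0; under 5.0 and 6.0 randomised against 600 mg od |
| Prior osimertinib (Protocol 4.2.1, 5.1) | first line only | first or second line under 5.0; first line under 6.0 and 7.0 |
| Liver disease exclusion and revised hepatotoxicity guidance (Protocol version history; 5.2, criterion 12) | in force | introduced at 7.0 |

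The combination rows in SAP 4.2.3 ask only for progression after osimertinib, so the first-line restriction does not carry over to them.

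**Crossover data.** SAP 2.2 keeps the data of a patient who crosses over under the initial allocation. Protocol 9.4.1 and SAP 3.1.1 stop placebo-arm data at the last assessment before the first combination dose. SAP 3.2.2.3 counts treatment-emergent events up to the last dose of any study treatment plus follow-up, and SAP 4.2.3.2 only flags post-crossover events in listings. On one reading, events on osimertinib would be counted in the placebo column.

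**Scale of the mixing.** Let w be the share of the combination row enrolled before version 7.0, and g the adverse event rate in those patients minus the rate in version 7.0 combination patients.

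- Pooled row rate = (version 7.0 rate) + w × g. The contrast with placebo therefore shifts by w × g from the version 7.0 contrast.
- Earlier patients: Protocol section 2 reports no new safety findings, "including at the 300 mg bid dose (n=37) with a median duration of exposure of" about 2.6 months, at the review of 27 August 2021. That count of 37 covers all MET levels and may have grown before version 7.0 began.
- Version 7.0 combination arm: redacted; 40 to 120 assumed.
- FISH10+ and/or IHC90+ row, which matches the placebo arm, assuming about half (18) of the 37 qualify: w = 18/(18+40) = 0.31, falling to 18/(18+120) = 0.13.
- FISH5+ and/or IHC50+ row, with all 37: w = 37/(37+40) = 0.48, falling to 37/(37+120) = 0.24.
- Shift in the matching row if g is 10 points (assumed): 0.31 × 10 = 3.1 points, falling to 0.13 × 10 = 1.3. If g is 20 points: 6.2 falling to 2.6.

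**Precision lost by using version 7.0 patients only**, with an assumed event rate of 40% in both arms and all 37 earlier patients pooled as the alternative. The 95% half-width is 1.96 × √(0.24/n₁ + 0.24/n₂).

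- Arms of 60 and 30: 21.5 points for version 7.0 only; 20.1 pooled (97 and 30).
- Arms of 100 and 50: 16.6 points for version 7.0 only; 15.9 pooled (137 and 50).

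**The case against.** The strongest reply is that no between-arm safety comparison is planned. The objective evaluates each regimen, the protocol asks for a described difference only for ORR, and Protocol 9.3 and 9.4.4 already fix the SAF over all versions, so the SAP follows the protocol. That stands as far as it goes: what is optional is a descriptive summary, not a test. It does not justify leaving out the description that matches the trial's own randomisation.

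Several stronger readings are tempting, and the documents do not support them.

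- *Everything is pooled.* It is not. Rows are by regimen, 300 mg bid was given only under versions 5.0 to 7.0, and a row at the higher MET cut-off is provided.
- *The earlier patients were not randomised.* They were randomised, but against 600 mg od and open label.
- *They have years more follow-up in which to accumulate events.* Summaries count treatment-emergent events, which end about 28 (+7) days after the last dose (SAP 3.2.2.3). Only time on treatment matters. Some discontinuation tables also use fixed windows: 6 weeks, and 6, 12 and 24 weeks for hypersensitivity and hepatotoxicity.
- *About half of the column is earlier patients.* The 48% arises only in the broader MET row and at the smallest assumed arm.
- *Version 7.0 tables would remove every difference.* Protocol 7.1 allows the combination, but not savolitinib monotherapy, to continue beyond progression, so exposure can still differ between the randomised arms.

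Two safeguards exist. The IDMC reviews version 7.0 safety in both arms once, at the futility analysis (Protocol 9.6), but that is not a reported table. The SAP's amendment history also names the mock table shells as the master source for outputs; they may already include by-arm tables, but they are not public and the SAP text does not commit to them.

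**Conclusion.** The point holds as a should-fix. The by-arm version 7.0 safety summary is optional, no other section commits it, and a difference between the two committed columns is partly confounded with protocol version and blinding. The confounding is partial because the version 7.0 combination patients are inside the pooled row. Its size cannot be computed. The illustrative share of 31% to 13% in the matching row rests on an assumed arm of 40 to 120 and on half of the 37 earlier patients qualifying, and the shift of about 1 to 6 points rests further on an assumed rate gap of 10 to 20 points.

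A reader might infer that the safety results would be invalid or that a planned comparison is biased. Neither follows: the all-version tables are sound as descriptions of each regimen, and no safety test is planned. The conflict over crossover data is a separate defect in the same tables. If it is resolved the wrong way, it would hide part of what osimertinib contributes.

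**What to change.** In SAP 4.2.3, change *may* to *will*. Adverse event, AESI, exposure, laboratory, ECG and vital-sign summaries should be produced by arm for dosed patients randomised under version 7.0, with placebo-arm data cut at the first combination dose. Keep the all-version SAF tables as by-regimen descriptions.

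Reconcile SAP 2.2 with SAP 3.1.1 and Protocol 9.4.1, so that events after crossover to osimertinib are not counted in the savolitinib + placebo column.

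Exposure-adjusted rates and risk differences could be added, but they are a matter of preference and the point does not depend on them.

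The cost is a short SAP edit and one more table set from data already collected. The numbers in those tables are smaller; under the assumed sizes above, the half-width of a contrast widens by 1.4 points (21.5 − 20.1) or 0.7 points (16.6 − 15.9).

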4.2.3.1 Exposure

Exposure will be presented based on TPAS and SAF Analysis Sets.

Actual and total treatment duration will be summarised by the following: mean, SD, minimum, maximum, median and number of observations, for both study treatments. In addition, the number and percentage of patients with dose modifications (interruptions and/or reductions) of savolitinib and osimertinib in the first 6 weeks and for the whole treatment period, respectively, will be presented. Note that dose re-assignment to 300 mg of savolitinib flat dosing is not considered a dose reduction.

Relative dose intensity will be summarised by descriptive statistics for both study treatments separately.

Dose change plots will be included showing savolitinib and osimertinib exposure for each patient. The figures will show duration of dose with indications for dose reductions, dose interruptions, overdoses,

dose re-assignment, discontinuation, and time of start and end of confirmed response when applicable.

A table of the number of treatment cycles started for each study treatment will also be provided.

Total amount of study treatment received will be listed by study treatments.

4.2.3.2 Adverse Event

Key guidelines for counting incidence proportions of adverse events are as follows:

- When a patient has the same AE reported multiple times during an analysis period based on SOC and PT, the patient will only be counted once within a level of MedDRA in an AE incidence table.
- When assessing investigator-reported relationship to study drug of the AEs, if an AE changes in causal relationship during an analysis period for a patient, the related event will be chosen. Related AEs will include those reported as related by the investigator and those with a missing relationship. AE with a missing relationship will be presented as related in summary tables but will be presented in the data listing with a missing relationship.
- When summarising intensity of the AEs, if an AE changes in CTCAE grade during an analysis period for a patient, the AE with the maximum CTCAE grade will be chosen. In case the AE term (SOC and PT) is reported more than once, one of them with missing grade, and at least another with non-missing grade, the maximum CTCAE grade will be chosen from the non-missing grade values and the missing grade can be ignored. If all are of missing grade, then the AE severity will be summarised in an additional “Unknown” intensity category.
- When summarising intensity for drug-related AEs, only drug-related AEs will be used in the analysis. If a patient has the same AE reported multiple times during an analysis period for a drug-related AE, the AE with the maximum CTCAE grade will be chosen.

The number and percentage of patients with TEAEs, as classified by SOC and PT, will be summarised for the Safety analysis set:

- Patients with TEAEs and the number of TEAEs
- TEAEs that are causally related to Osimertinib, causally related to Savolitinib, and casually related to either Osimertinib or Savolitinib,
- TEAEs of CTCAE grade ≥ 3
- TEAEs of CTCAE grade ≥ 3 related to Osimertinib or related to Savolitinib
- TEAEs by common frequency ($>5\%$) in descending order
- TEAEs by maximum CTCAE grade
- TEAEs with death outcome
- Non-serious TEAEs that occurred in greater than 5% of patients

- Serious TEAEs
- Serious TEAEs – key patient information
- Serious TEAEs that are assessed by investigator as causally related to Osimertinib, causally related to Savolitinib, and casually related to either Osimertinib or Savolitinib
- TEAEs leading to dose modification of each study treatment
- TEAEs leading to discontinuation of each study treatment (overall and within the first 6 weeks)
- TEAEs leading to discontinuation of each study treatment - key patient information
- Other significant TEAEs
- Other significant TEAEs leading to discontinuation of each study treatment (overall and within the first 6 weeks)
- TEAEs of special interest
- TEAEs of special interest by CTCAE grade
- TEAEs of special interest leading to discontinuation of each study treatment (overall and within the first 6 weeks)
- Hypersensitivity/anaphylaxis and hepatotoxicity TEAEs of special interest leading to discontinuation of savolitinib (overall and within the first 6, 12 and 24 weeks)

An overall summary table of the number of patients experiencing at least one adverse event will be produced. An overall summary table of the number of AEs will also be provided.

TEAEs in any category, including AESI, TEAEs of CTCAE grade ≥ 3 , deaths, SAEs, TEAEs leading to discontinuation, and other significant TEAEs will be summarised.

AEs occurring prior to first dose of study treatments (i.e., before study Day 1) which subsequently worsen in severity following dosing will be presented in the summary tables. All other AEs occurring prior to first dose of study treatments (i.e., before study Day 1), or after the 35-day follow-up period (28 days allowing for the ± 7 -day window) after discontinuation of study treatments will be listed, but not included in the summaries.

Details of any deaths will be listed for all patients.

All AEs will be listed, and any AEs started on or after a patient took osimertinib after crossing over from 300 mg bid + placebo to 300 mg bid + osimertinib will be flagged.

